## 11.5 Extent of Exposure (Product Consumption)

Details of the product test prior to enrolment and of product use after randomization will be listed by sequence for the Safety population.

The number and percentage of subjects who smoked 1, 2, or 3 (categories of 0 and >3 will be included if applicable) THS Menthol Tobacco Stick at admission will be tabulated; together with the number and percentage of subjects who performed the NNS product trial with 2 number of sprays (categories of 0, 1, >2 will also be included if applicable).

The number and percentage of subjects who smoked 0 or 1 (category >1 will also be included if applicable) THS Menthol Tobacco Stick, or mCC during single use days (Day 1 or Day 3) will be tabulated by sequence; together with the number and percentage of subjects who performed the single use day of the NNS product with 0 or 2 number of sprays (categories of 1, >2 will be included if applicable).

The data will be presented in the below outputs:

TFL number	Title
TABLES	
15.2.2.1	Descriptive Statistics of Product Use - Safety Population
LISTINGS	
15.3.2.1	Listing of Product Usage
15.3.2.2	Listing of Cigarette Butt and Menthol Tobacco Stick Collection Data

## 11.6.2 Secondary Analyses

### 11.6.2.1 Pharmacokinetics

The secondary PK parameters from Group-1 PK population ( $AUC_{(0-t)}$ ,  $AUC_{(0-\infty)}$ ,  $\%AUC_{extrap}$ ,  $t_{last}$ ,  $t_{max}$ ,  $\lambda_z$  and  $t_{1/2}$ ) and the PK parameters from Group-2 PK population ( $C_{max}$ ,  $AUC_{(0-last)}$ ,  $AUC_{(0-\infty)}$ ,  $\%AUC_{extrap}$ ,  $t_{last}$ ,  $t_{max}$ ,  $\lambda_z$  and  $t_{1/2}$ ) will be listed and summarized as described in Section 11.1 “General Considerations” and subsections. In addition plots of the data versus product will be provided.

The nicotine plasma concentrations will be summarized in a similar manner to the PK parameters but will also be split out by sample time point. Geometric mean (95% CI) profiles, spaghetti plots of all subjects and individual PK profiles for each subject will also be presented.

PK parameter and plasma concentration data will also be listed along with the details of the actual times after  $T_0$ .

TFL number	Title
TABLES	
15.2.4.5	Descriptive Statistics of Pharmacokinetic Parameters of Nicotine – PK Population

TFL number	Title
15.2.4.5.1	Descriptive Statistics of Pharmacokinetic Parameters of Nicotine by Sex – PK Population
15.2.4.5.2	Descriptive Statistics of Pharmacokinetic Parameters of Nicotine by Nicotine Level – PK Population
15.2.4.6	Descriptive Statistics of Plasma Nicotine Concentrations (ng/mL) – PK Population
15.2.4.6.1	Descriptive Statistics of Plasma Nicotine Concentrations (ng/mL) by Sex – PK Population
15.2.4.6.2	Descriptive Statistics of Plasma Nicotine Concentrations (ng/mL) by Nicotine Level – PK Population
FIGURES	
15.1.2.1.1	Nicotine Plasma Concentration (ng/mL) Profiles Geometric Mean ( $\pm$ 95% CI) – Group-1 PK Population
15.1.2.1.2	Nicotine Plasma Concentration (ng/mL) Profiles Geometric Mean ( $\pm$ 95% CI) – Group-2 PK Population
15.1.2.2.1	Nicotine Plasma Concentration (ng/mL) Profiles for All Subjects – Group-1 PK Population
15.1.2.2.2	Nicotine Plasma Concentration (ng/mL) Profiles for All Subjects – Group-2 PK Population
15.1.2.3	Nicotine Plasma Concentration (ng/mL) Profiles by Subject – PK Population
15.1.2.4	Secondary Pharmacokinetic Parameters of Nicotine – Group-1 PK Population
15.1.2.5	Pharmacokinetic Parameters of Nicotine – Group-2 PK Population
LISTINGS	
15.3.3.1	Listing of Pharmacokinetic Parameters of Nicotine
15.3.3.2	Listing of Plasma Nicotine Concentrations (ng/mL) and Sampling Times
15.3.3.3	Listing of Additional Pharmacokinetic Parameter Data

## 11.6.2.1.1 THS 2.2 Menthol vs mCC

Only subjects in the Group-1 PK population will be included in the following analyses.

- The secondary analysis of  $AUC_{(0-\infty)}$ ,  $AUC_{(0-t)}$  and  $t_{1/2}$  will be performed on the natural log-transformed parameters using the same ANOVA model as used for the primary analysis. (Section 11.6.1 "Primary Analyses"). Only subjects in the Group 1 PK population who provide evaluable data for both the THS 2.2 Menthol and mCC products will be included in the analyses.

Supportive analysis will be performed as described in Section 11.6.3 "Supportive/Sensitivity Analysis" in order to evaluate the sensitivity of THS 2.2 effect estimates to methods used for missing data by means of a mixed model approach, should there be 20% or more missing PK parameters.

- The analysis of  $t_{max}$  will be performed by calculating the difference for each subject (THS 2.2 Menthol - mCC) and obtaining the Hodges-Lehmann (**Hodges and Lehmann, 1963**) 95% CI estimates. The median  $t_{max}$  for each product and the median difference between the products along with the 95% CI will be presented in the tables. Supportive analysis will be performed as described in Section 11.6.3 "Supportive/Sensitivity Analysis" in order to evaluate the THS 2.2 effect estimates on  $t_{max}$  adjusted for period, sequence, and subject within sequence.

The data will be presented in the below outputs:

TFL number	Title
TABLES	
15.2.4.1	Analysis of Secondary Pharmacokinetic Parameters of Nicotine – Group-1 PK Population

#### 11.6.2.1.2 THS 2.2 Menthol vs NNS

The following analyses will be conducted in only Group-2 PK population:

- The secondary analysis of  $C_{max}$ ,  $AUC_{(0-last)}$ ,  $AUC_{(0-\infty)}$ ,  $AUC_{(0-t')}$  and  $t_{1/2}$  parameters will be performed using the same ANOVA model as used for the primary analysis (Section 11.6.1 "Primary Analyses").

Only subjects in the Group-2 PK population who provide evaluable data for both the THS 2.2 Menthol and mCC products will be included in the analyses.

The analysis of  $C_{max}$  and  $AUC_{(0-last)}$  will test if the lower bound of the 95% CI for the ratio (THS 2.2 Menthol : NNS) is  $> 1.0$  at the 0.025 level of significance in order to determine if the rate and the amount of nicotine absorbed of the THS 2.2 Menthol is higher relative to NNS. This approach will be used to test the following hypothesis for both  $C_{max}$  and  $AUC_{(0-last)}$  parameters:

$$H_0: X_{THS} / X_{NNS} = 1.0$$

$$H_A: X_{THS} / X_{NNS} > 1.0$$

where  $X_{THS}$  and  $X_{NNS}$  are the adjusted geometrical means of THS 2.2 Menthol and NNS, respectively.  $H_0$  is rejected with a type I error  $\alpha = 0.025$  (one-sided test).

- To test if the time to the maximum nicotine concentration in THS 2.2 Menthol is shorter than in NNS the following hypothesis will be evaluated:

$$H_0: X_{THS} - X_{NNS} = 0$$

$$H_A: X_{THS} - X_{NNS} < 0$$

where  $X_{THS}$  and  $X_{NNS}$  are the median values of the THS 2.2 Menthol and NNS, respectively.  $t_{max}$  will be analysed on the original scale using the Wilcoxon Signed-Rank Test with a type I error  $\alpha = 0.025$  (one-sided test), as values are ordinal/discrete, and the assumption of normality may be questionable.

The analysis of  $t_{max}$  will be performed by calculating the difference for each subject (THS 2.2 Menthol - NNS) and obtaining the Hodges-Lehmann 95% CI estimates (**Hodges and Lehmann, 1963**). The median  $t_{max}$  for each product and the median difference between the products along with the 95% CI will be presented.

Supportive analysis will be performed as described in Section 11.6.3 "Supportive/Sensitivity Analysis".

The data will be presented in the below outputs:

TFL number	Title
TABLES	
15.2.4.2	Analysis of Pharmacokinetic Parameters of Nicotine – Group-2 PK Population

11.6.2.2 Biomarkers

11.6.2.2.1 Exhaled CO and COHb

COHb measured in blood and exhaled CO will be investigated as a measure of exposure to CO.

CO in exhaled breath will be measured using the Smokerlyzer® device, such as the Micro+™ Smokerlyzer® device or similar, once on Day -1 and Day 4. On Days 1 and 3, the first test per day will be performed within 15 minutes prior to  $T_0$  and then between 12:00 PM and 01:30 PM, between 4:00 PM and 05:30 PM, and between 8:00 PM and 09:30 PM. On the wash-out days (Day 0 and Day 2) it will be conducted between 08:00 AM and 09:30 AM, 12:00 PM and 01:30 PM, between 4:00 PM and 05:30 PM, and between 8:00 PM and 09:30 PM.

Analysis of the COHb measurement will be performed at a local laboratory using blood samples taken at specified timepoints. A total of 5 blood samples will be taken per single use day. The first sample will be taken within 15 minutes prior to  $T_0$ . Thereafter the sampling times in relation to  $T_0$  are at 15 minutes, 60 minutes, 4 hours, 12 hours post  $T_0$ .

Descriptive statistics summarized by exposure will be produced separately for all scheduled timepoints for exhaled CO and COHb assessments at single use day. This will be done on the PK populations, overall and by the two stratification factors (sex, mCC nicotine level at Admission) as specified in Section 11.1.1 "Stratified Presentation".

Actual values of blood COHb and levels of exhaled CO will be listed and summarized. The number of subjects with COHb levels  $\leq 2\%$  will be summarized for each measurement. The 2% threshold is important because, as reported in (**WHO, 2010**), COHb elevated above 2% was found to cause ST-segment changes and decreased time to angina.

In addition line graphs will be produced for exposure means (and 95% CI) over all timepoints.

Values of exhaled CO measured during wash-out, Admission, and discharge will not be analyzed because they will be collected only for monitoring purposes, however they will be reported as described in Section 11.4 “Measurements of Product Compliance”.

The analysis of the exhaled CO during single use and log transformed blood COHb levels will be performed using a mixed effects ANOVA with a restricted maximum likelihood (REML) method to estimate mean differences and variances separately for THS 2.2 Menthol vs mCC and THS 2.2 Menthol vs NNS, using heterogeneous compound symmetry covariance structure in order to allow unequal variances at the different timepoints (**Brown and Prescott, 1999**). Subject nested within sequence will be used as a random effect and sequence, period, product and product\*time point as fixed effect factors. The model will be evaluated including all of the different assessment timepoints, excluding the assessment prior to  $T_0$ . In addition, time point will be treated as a repeated measurement.

The SAS code to be used is shown below:

```
Proc mixed data=_data_ method=reml maxiter=200;
  Class subject sequence product period;
  Model log_COHb (or CO) = sequence period product time_point
    product*time_point;
  Random subject(sequence);
  Repeated time_point / subject=subject*product type=csh;
  Lsmean product / pdiff =control('mCC/NNS') alpha=0.05 cl;
  Lsmean product*time_point / pdiff alpha=0.05 cl;
  Run;
```

In case of model convergence issues, this will be reported in the study report and additional covariance structures will be investigated with the following order: heterogeneous autoregressive(type=arh), variance component (type=vc), and unstructured (type=un).

For the analysis of CO breath test, the main comparison will be the difference over all time points. LS means for each product, the overall difference (THS 2.2 Menthol - mCC or THS 2.2 Menthol - NNS as appropriate) and the differences at each time point will be presented in the tables as a point and interval (95% CI) estimate. Figures of the LS mean difference and 95% CI at each time point will be produced.

For the COHb analysis, the main comparison will be the ratio over all time points. LS means for each product will be back-transformed by exponentiation and presented in tables together with the point and interval (95% CI) estimate of the overall ratio (THS 2.2 Menthol:mCC or THS 2.2 Menthol:NNS as appropriate) and of the ratios at the different time points. Figures of the LS mean ratio and 95% CI at each time point will be produced.

The data will be presented in the below outputs:

TFL number	Title
TABLES	
15.2.4.7	Analysis of Blood COHb (%) – PK Population
15.2.4.8.1	Descriptive Statistics of Blood COHb (%) Continuous Measurements – PK Population
15.2.4.8.1.1	Descriptive Statistics of Blood COHb (%) by Sex – PK Population
15.2.4.8.1.2	Descriptive Statistics of Blood COHb (%) by Nicotine Level – PK Population
15.2.4.8.2	Descriptive Statistics of Blood COHb (%) Categorical Measurements – PK Population
15.2.4.9	Analysis of Exhaled CO (ppm) During Single Use – PK Population
15.2.4.10.1	Descriptive Statistics of Exhaled CO (ppm) During Single Use Continuous Measurements – PK Population
15.2.4.10.1.1	Descriptive Statistics of Exhaled CO (ppm) During Single Use by Sex – PK Population
15.2.4.10.1.2	Descriptive Statistics of Exhaled CO (ppm) During Single Use by Nicotine Level – PK Population
15.2.4.10.2	Descriptive Statistics of Exhaled CO (ppm) During Single Use Categorical Measurements – PK Population
15.2.4.11.1	Descriptive Statistics of Exhaled CO (ppm) During Days -1, 0, 2 and 4 Continuous Measurements – PK Population
15.2.4.11.1.1	Descriptive Statistics of Exhaled CO (ppm) During Days -1, 0, 2 and 4 by Sex – PK Population
15.2.4.11.1.2	Descriptive Statistics of Exhaled CO (ppm) During Days -1, 0, 2 and 4 by Nicotine Level – PK Population
15.2.4.11.2	Descriptive Statistics of Exhaled CO (ppm) During Days -1, 0, 2 and 4 Categorical Measurements – PK Population
FIGURES	
15.1.2.6.1	Blood COHb (%) Profiles Geometric Mean ( $\pm$ 95% CI) – Group-1 PK Population
15.1.2.6.2	Blood COHb (%) Profiles Geometric Mean ( $\pm$ 95% CI) – Group-2 PK Population
15.1.2.7.1	Blood COHb (%) Profiles Geometric Least Squares Mean Ratio ( $\pm$ 95% CI) – Group-1 PK Population
15.1.2.7.2	Blood COHb (%) Profiles Geometric Least Squares Mean Ratio ( $\pm$ 95% CI) – Group-2 PK Population
15.1.2.8.1	Exhaled CO (ppm) Profiles During Single Use Arithmetic Mean ( $\pm$ 95% CI) – Group-1 PK Population
15.1.2.8.2	Exhaled CO (ppm) Profiles During Single Use Arithmetic Mean ( $\pm$ 95% CI) – Group-2 PK Population
15.1.2.9.1	Exhaled CO (ppm) Profiles During Single Use Arithmetic Least Squares Mean Differences ( $\pm$ 95% CI) – Group-1 PK Population

TFL number	Title
15.1.2.9.2	Exhaled CO (ppm) Profiles During Single Use Arithmetic Least Squares Mean Differences ( $\pm$ 95% CI) – Group-2 PK Population
LISTINGS	
15.3.3.4	Listing of Blood COHb Levels (%) and Sampling Times
15.3.3.5	Listing of Exhaled Breath CO (ppm) and Measurement Times

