### 5.2 Secondary Objectives and Endpoints

1. To determine if  $C_{max}$  and  $AUC_{(0-last)}$  of the THS 2.2 Menthol are higher relative to nicotine nasal spray (NNS) following single use of the THS 2.2 Menthol and NNS.

Endpoints:

- $C_{max}$  [NNS and THS 2.2 Menthol, Group-2]
- $AUC_{(0-last)}$  [NNS and THS 2.2 Menthol, Group-2]

2. To evaluate the difference on nicotine pharmacokinetic (PK) absorption parameters (AUC from start of product use extrapolated to time of last quantifiable concentration to infinity [ $AUC_{(0-\infty)}$ ] and partial AUC, where  $t'$  is the subject-specific time of maximum nicotine concentration following single use of the mCC or NNS product [ $AUC_{(0-t')}$ ]) between the THS 2.2 Menthol and mCC, as well as the THS 2.2 Menthol and NNS.

Endpoints:

- $AUC_{(0-\infty)}$ .
- Partial  $AUC_{(0-t')}$ .

3. To evaluate the time to the maximum concentration ( $t_{max}$ ) of nicotine for the THS 2.2 Menthol as compared to mCC and to determine if the  $t_{max}$  for THS 2.2 Menthol is shorter as compared to NNS.

Endpoint:

- $t_{max}$ .

4. To describe the terminal half-life ( $t_{1/2}$ ) of nicotine for the THS 2.2 Menthol, mCC, and NNS.

Endpoint:

- $t_{1/2}$ .

5. To describe the differences on urge-to-smoke over time between the THS 2.2 Menthol and mCC, as well as between the THS 2.2 Menthol and NNS.

Endpoints:

Urge-to-smoke as measured with the Questionnaire of Smoking Urges brief (QSU-brief) (Cox et al, 2001).

- Total score.
- Factor-1.
- Factor-2.

6. To describe product evaluation in the THS 2.2 Menthol and mCC users.

Endpoints:

Product evaluation as measured with the Modified Cigarette Evaluation Questionnaire (MCEQ) (Cappelleri et al, 2007) [mCC and THS 2.2 Menthol, in Group-1].

- Smoking Satisfaction subscale.
- Enjoyment of Respiratory Tract Sensation subscale.
- Psychological Reward subscale.
- Aversion subscale.
- Craving Reduction subscale.

7. To describe the levels of carbon monoxide (CO) exposure for the THS 2.2 Menthol, as compared to mCC and NNS users.

Endpoints:

- Levels of exhaled CO.
- Carboxyhemoglobin (COHb) in blood.

8. To describe the plasma levels of cotinine in the THS 2.2 Menthol, mCC, and NNS.

Endpoints:

- Levels of cotinine in plasma.

9. To monitor the safety during the study.

Endpoints:

- Incidence of adverse events (AEs)/serious adverse events (SAEs) and device events, including THS 2.2 Menthol malfunction/misuse.

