## 11.6.2.3 Questionnaires

## 11.6.2.3.1 Urge-to-Smoke Questionnaire of Smoking Urges Brief

The total score and the two factors from the QSU-brief will be listed for all scheduled time points and summarized overall and by the two stratification factors (sex, mCC nicotine level at Admission) for the PK populations, as specified in Section 11.1.1 “Stratified Presentation”. The individual responses to all questions will be listed by product, study day, and assessment time points.

In addition line graphs will be produced for the total score and factors means (and 95% CI) over all timepoints.

The analysis of the subjective effects of smoking (the total score, and Factor-1 and Factor-2 from the QSU-brief) will be performed using the same mixed effects ANOVA adopted for the analysis of CO breath test described in Section 11.6.2.2.1 "Exhaled CO and COHb".

A sensitivity analysis using bootstrap techniques, will also be conducted on the total and factors score of QSU-brief, as described in Section 11.6.3 "Supportive/Sensitivity Analysis".

The main comparison will be the mean difference over all timepoints. LS means for each product, the overall mean difference (THS 2.2 Menthol - mCC or THS 2.2 Menthol - NNS as appropriate) and the mean differences at each time point will be presented in the tables as a point and interval (95% CI) estimate. Figures of the LS mean difference and 95% CI at each time point will be produced.

The data will be presented in the below outputs:

TFL number	Title
TABLES	
15.2.4.12	Analysis of QSU-brief Questionnaire Factors and Total Score – PK Population
15.2.4.14	Descriptive Statistics of QSU-brief Questionnaire Factors and Total Score – PK Population
15.2.4.14.1	Descriptive Statistics of QSU-brief Questionnaire Factors and Total Score by Sex – PK Population
15.2.4.14.2	Descriptive Statistics of QSU-brief Questionnaire Factors and Total Score by Nicotine Level – PK Population
FIGURES	
15.1.2.10.1	QSU-brief Factors and Total Score Profiles Arithmetic Mean ( $\pm$ 95% CI) – Group-1 PK Population
15.1.2.10.2	QSU-brief Factors and Total Score Profiles Arithmetic Mean ( $\pm$ 95% CI) – Group-2 PK Population
15.1.2.11.1	QSU-brief Factors and Total Score Profiles Arithmetic Least Squares Mean Differences ( $\pm$ 95% CI) – Group-1 PK Population
15.1.2.11.2	QSU-brief Factors and Total Score Profiles Arithmetic Least Squares Mean Differences ( $\pm$ 95% CI) – Group-2 PK Population
LISTINGS	

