To evaluate the sensitivity to the distributional assumptions for the QSU-brief (see Section 11.6.2.3.1 “Urge-to-Smoke Questionnaire of Smoking Urges Brief”) and MCEQ (see Section 11.6.2.3.2 “Modified Cigarette Evaluation Questionnaire”) questionnaire scores, point and 95% interval estimates will also be assessed by means of the percentile bootstrap technique, using 2000 bootstrap samples which preserve the number of subjects per sequence. The data will be presented in the below outputs:

TFL number	Title
TABLES	
15.2.4.3.1	Supportive Analysis of Pharmacokinetic Parameters of Nicotine Excluding Subjects with $T_0$ Value $>5\%$ of Their $C_{max}$ Value – PK Population
15.2.4.3.2	Analysis of Pharmacokinetic Parameters of Nicotine by Bootstrapping Techniques – PK Population
15.2.4.4	Analysis of Pharmacokinetic Parameters of Nicotine by Zero Sec Imputation – PK Population
15.2.4.13	Analysis of QSU-brief Questionnaire Factors and Total Score by Bootstrapping Techniques – PK Population
15.2.4.16	Analysis of MCEQ Subscales by Bootstrapping Techniques – PK Population

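### The mixed model for COHb, exhaled CO and QSU-brief names no degrees-of-freedom method, so its main 95% CIs are about 2–8% too narrow; its code also omits time_point from CLASS and lists an unsafe fallback covariance.

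*SAP*

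**What the plan says.** SAP 11.6.2.2.1 prints the code for log COHb and exhaled CO. Its classification line is "Class subject sequence product period". Further down, time_point appears in the MODEL statement, in LSMEANS product*time_point and as the repeated effect: "Repeated time_point / subject=subject*product type=csh". Subject within sequence is the only random effect, and the MODEL statement carries no options.

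If the heterogeneous compound-symmetry (CSH) structure does not converge, the stated order is "heterogeneous autoregressive(type=arh), variance component (type=vc), and unstructured (type=un"). The section adds: "In case of model convergence issues, this will be reported in the study report".

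The headline result is the product contrast averaged over time: "For the COHb analysis, the main comparison will be the ratio over all time points". Exhaled CO is treated likewise, as a difference. SAP 11.6.2.3.1 says the QSU-brief analysis "will be performed using the same mixed effects ANOVA adopted for the analysis of CO breath test".

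**The concern.** The contrast that matters compares two products, each used in a different period by the same subject. Sampling more often within a period describes that period better but adds no further independent comparisons between periods. A model that credits the product effect with all the residual degrees of freedom counts repeated samples as if they did, and its t quantile is too small. This bites hardest in Group-2, where the right df are only about 14 to 16.

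The fallback is a different and potentially larger problem. With type=vc and only a subject random effect, time points in the same subject-period are treated as independent given the subject. The correlation that the subject effect induces across both periods is kept, but the extra correlation within a period is lost. That extra correlation sets the standard error of the product contrast. Because vc will normally converge, type=un after it would rarely be reached.

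At stake are the interval estimates that the SAP names as the main comparison for three sets of secondary endpoints.

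**Working it through.** **Inputs.** Group sizes are 44 and 18 with 10% dropout (SAP 8), so about 40 and 16 completers (44 × 0.9 = 39.6; 18 × 0.9 = 16.2). With the pre-T0 value excluded (SAP 11.6.2.2.1), the number of modelled time points T is 3 for exhaled CO, 4 for COHb and 9 for QSU-brief. The documents state no df for these models. That PROC MIXED defaults to containment when a RANDOM statement is present is an assumption about the software. Time_point is taken as added to CLASS, since otherwise nothing runs.

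**Reference df from the SAP's own primary model.** The PROC GLM in SAP 11.6.1 has one value per period: 2n observations and rank n + 2, so product has 2n − (n + 2) = n − 2 df.

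**Default df here.** Subject(sequence) does not contain product, so product receives N − rank[X Z] = 2nT − [n + 2 + 2(T − 1)]. For n = 16, T = 4: 128 − 24 = 104.

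Narrowing = 1 − t(0.975, default df)/t(0.975, n − 2). For n = 16, T = 9: 1 − 1.9693/2.1448 = 8.2%. Coverage = 1 − 2·P[t(n − 2) > t(0.975, default df)].

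| n | Correct df | Default df (CO / COHb / QSU) | CI too narrow, % | Coverage, % |
|---|---|---|---|---|
| 16 | 14 | 74 / 104 / 254 | 7.1 / 7.5 / 8.2 | 93.4 / 93.3 / 93.1 |
| 18 | 16 | 84 / 118 / 288 | 6.2 / 6.6 / 7.2 | 93.6 / 93.5 / 93.3 |
| 40 | 38 | 194 / 272 / 662 | 2.6 / 2.7 / 3.0 | 94.4 / 94.4 / 94.3 |
| 44 | 42 | 214 / 300 / 730 | 2.3 / 2.5 / 2.7 | 94.5 / 94.4 / 94.4 |

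**Check by simulation.** REML fits of the specified model to COHb-like data (assumed within-period correlation 0.5) gave these results:

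- n = 18, 1,500 runs: effective df about 16, not 118; coverage 93.7% with the default and 95.6% with n − 2.
- n = 44, 700 runs: effective df about 46, not 300. Coverage was 95.6% with the default and 96.1% with n − 2, so a loss as small as the table's is not visible in that many runs.
- n = 16: the model standard error tracked the empirical one (T = 3: 0.270 against 0.266; T = 4: 0.260 against 0.265). On the specified path only the quantile is wrong. All 1,100 of these fits converged, with a general optimiser rather than SAS.

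**The vc branch.** Let ρ be the within-period correlation beyond the subject effect; it is not in the documents. With total residual variance 1, the between-period mean square has expectation 1 + (T − 1)ρ on n − 2 df. The within-period mean square has expectation 1 − ρ on 2(n − 1)(T − 1) df. The vc model pools them.

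For COHb, n = 16, ρ = 0.4: (14 × 2.2 + 90 × 0.6)/104 = 0.815, where 2.2 is needed. The SE ratio is √(0.815/2.2) = 0.61.

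| n = 16 | SE as a fraction of true, ρ = 0.2 / 0.4 / 0.6 | Two-sided error at nominal 5% |
|---|---|---|
| Exhaled CO | 0.81 / 0.68 / 0.58 | 11 / 18 / 25% |
| COHb | 0.75 / 0.61 / 0.51 | 14 / 23 / 32% |
| QSU-brief | 0.59 / 0.44 / 0.35 | 25 / 39 / 50% |

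With n = 40 the figures are almost the same. At ρ = 0 the vc standard error is unbiased.

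**The case against.** The printed block is a template: its response is given as COHb or CO and its control level as mCC/NNS, so it was never going to run verbatim. The prose treats time point as a repeated factor and product by time point as a fixed effect. The missing CLASS entry is therefore clerical. That stands.

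The upper end of the range belongs to one case, QSU-brief in Group-2 with 16 completers. Group-1, which carries the primary comparison, loses only 2–3%. That stands too, and the two groups should be quoted separately.

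The vc problem needs both CSH and the autoregressive structure to fail. CSH converged in every simulated fit above, and the SAP requires convergence trouble to be reported. The error rates rest on assumed correlations. All of this is fair, so the vc figures describe a contingency and not an expected result.

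Finally, no decision depends on these intervals. The CO objective is "To describe the levels of carbon monoxide (CO) exposure for the THS 2.2 Menthol, as compared to mCC and NNS users", SAP 11.1.7 makes no claims from individual tests, and the primary analysis is untouched. For QSU-brief, SAP 11.6.3 adds that "point and 95% interval estimates will also be assessed by means of the percentile bootstrap technique", which resamples within sequence and is a partial check, though it does not cure small-sample narrowing. COHb and exhaled CO have no such check.

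These points limit the importance of the matter. They do not make the default df right.

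**Conclusion.** The concern holds and is minor. Followed as written, with time_point restored to CLASS, the main product CIs for COHb, exhaled CO and QSU-brief are 6.2–8.2% too narrow in Group-2 and 2.3–3.0% too narrow in Group-1. Coverage runs from 93.1% to 94.5%. This rests on the containment default and on n − 2 as the reference df, which the SAP's own primary model and the simulations support. The vc fallback could understate the standard error far more, but only if two earlier structures fail and the within-period correlation is material. The CLASS omission is a coding slip with no effect on any estimate. The Cmax and AUC analyses are unaffected.

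**What to change.** Make three edits to SAP 11.6.2.2.1; they carry over to QSU-brief by reference.

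1. Add time_point to the CLASS statement.
2. Add ddfm=kr (or ddfm=satterth) to the MODEL statement.
3. In the fallback list, replace type=vc with type=cs on REPEATED, keeping random subject(sequence). Equivalently, use random subject(sequence) and product*subject(sequence) with an independent residual. Do not combine a product*subject(sequence) term with a compound-symmetric residual: the two are not separately identifiable. For example, variances of 0.3 and 0.1 give the same covariance block as 0.1 and 0.3.

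No extra data are needed. The intervals widen by about 6.6–8.9% in Group-2 (for example 2.1448/1.9693 − 1 = 8.9%) and 2.4–3.1% in Group-1.
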